8.1.3. Clinical Evaluation

8.1.3.1. Clinical Signs and Symptom Scores, Clinical Outcomes, and Clinical Response

Clinical signs and symptoms of acute cystitis will be recorded based on participant interview per the SoA (Section 1.3) using the scoring system and instructions in [Appendix 6](#). At Baseline, the participant must present with at least 2 signs and symptoms and have a total cumulative symptom score ≥ 2 . At TOC, success is defined as normal presentation of signs and symptoms with a total cumulative symptom score of zero and no new signs and symptoms of the infection under study.

A study physician or otherwise appropriately medically trained staff will determine the individual clinical signs and symptoms scores for acute cystitis ([Appendix 6](#)) at the On-therapy, TOC, and Follow-up Visits. The same scorer will be used at all assessment

time points for each participant, on all occasions, whenever possible. The score will be used to programmatically determine the clinical outcome at the On-therapy Visit (Table 9) and the clinical outcome and response (success or failure) at the TOC Visit (Table 10) and the Follow-up Visit (Table 11).

Table 9 Clinical Outcome at the On-Therapy Visit

Defining Criteria	Outcome^a
Resolution of signs and symptoms of acute cystitis present at Baseline (and no new signs and symptoms), without the participant receiving other systemic antimicrobials before the On-therapy Visit	Clinical resolution
Improvement in total symptom scores from Baseline, but not complete resolution, without the participant receiving other systemic antimicrobials before the On-therapy Visit	Clinical improvement
Worsening or no change in total symptom scores from Baseline or the participant received other systemic antimicrobials for the current infection prior to or on the date of the On-therapy Visit	Clinical worsening
1) The Baseline score is missing, or 2) The On-therapy assessment is missing, or 3) The participant received other systemic antimicrobials not for the current infection prior to the assessment (unless clinical worsening outcome criteria were met)	Unable to determine

- a. A study physician or otherwise appropriately medically trained staff will determine the individual clinical signs and symptoms scores for acute cystitis (Appendix 6), which will then be used to programmatically determine the clinical outcome. The same scorer will be used at all assessment time points for each participant, on all occasions, whenever possible.

Table 10 Clinical Outcome and Response at the Test-of-Cure Visit

Defining Criteria	Outcome^a	Response
Resolution of signs and symptoms of acute cystitis present at Baseline (and no new signs or symptoms), without the participant receiving other systemic antimicrobials before the TOC Visit	Clinical resolution	Clinical success
Improvement in total symptom scores from Baseline, but not complete resolution, without the participant receiving other systemic antimicrobials before the TOC Visit	Clinical improvement	Clinical failure
Worsening or no change in total symptom scores from Baseline or the participant received other systemic antimicrobials for the current infection before or on the date of the TOC Visit	Clinical worsening	Clinical failure
1) The Baseline score is missing, or 2) The TOC assessment is missing, or 3) The participant received other systemic antimicrobials not for the current infection prior to the assessment (unless clinical worsening criteria were met)	Unable to determine	Clinical failure

TOC = Test-of-Cure

- a. A study physician or otherwise appropriately medically trained staff will determine the individual clinical signs and symptoms scores for acute cystitis ([Appendix 6](#)), which will then be used to programmatically determine the clinical outcome. The same scorer will be used at all assessment time points for each participant, on all occasions, whenever possible.

Table 11 Clinical Outcome and Response at the Follow-up Visit

Defining Criteria	Outcome^a	Response
Resolution of signs and symptoms of acute cystitis demonstrated at the TOC Visit persist at the Follow-up Visit (and no new signs and symptoms), without the participant receiving other systemic antimicrobials before the Follow-up Visit	Sustained clinical resolution	Clinical success
Resolution of signs and symptoms of acute cystitis present at Baseline (and no new signs or symptoms), after clinical failure at TOC, without the participant receiving other systemic antimicrobials before the Follow-up Visit	Delayed clinical resolution	Clinical failure
Improvement in total symptom scores from Baseline, but not complete resolution, without the participant receiving other systemic antimicrobials before the Follow-up Visit	Clinical improvement	Clinical failure
Worsening or no change in total symptom scores at Follow-up compared to Baseline after clinical failure at TOC, or the participant received other systemic antimicrobials for the current infection before or on the date of the Follow-up Visit	Clinical worsening	Clinical failure
Signs and symptoms of acute cystitis reoccur at the Follow-up Visit after clinical success at TOC	Clinical recurrence	Clinical failure
1) The Baseline score is missing, or 2) The Follow-up assessment is missing, or 3) The participant received other systemic antimicrobials not for the current infection prior to the assessment (unless the clinical worsening or recurrence outcome criteria were met)	Unable to determine	Clinical failure

TOC = Test-of-Cure

- a. A study physician or otherwise appropriately medically trained staff will determine the individual clinical signs and symptoms scores for acute cystitis ([Appendix 6](#)), which will then be used to programmatically determine the clinical outcome. The same scorer will be used at all assessment time points for each participant, on all occasions, whenever possible.

CCI

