Clinical response at the TOC and Follow-up Visits	Female participants with acute cystitis	Gepotidacin 1500 mg BID for 5 days versus nitrofurantoin 100 mg BID for 5 days, regardless of adherence	See Table 10 and Table 11	Absolute difference in the clinical success rate in the gepotidacin and nitrofurantoin treatment groups	Study treatment discontinuation (due to any reason) – treatment policy Use of systemic antimicrobials – composite strategy
Clinical outcome at the TOC and Follow-up Visits	Female participants with acute cystitis	Gepotidacin 1500 mg BID for 5 days versus nitrofurantoin 100 mg BID for 5 days, regardless of adherence	See Table 10 and Table 11	Percentage of participants in each outcome category in the gepotidacin and nitrofurantoin arms separately	Study treatment discontinuation (due to any reason) – treatment policy Use of systemic antimicrobials – composite strategy
Clinical response at the TOC and Follow-up Visits	Female participants with acute cystitis with qualifying bacterial uropathogen(s) at Baseline that all are susceptible to nitrofurantoin	Gepotidacin 1500 mg BID for 5 days versus nitrofurantoin 100 mg BID for 5 days, regardless of adherence	See Table 5	Absolute difference in the clinical success rate in the gepotidacin and nitrofurantoin treatment groups	Study treatment discontinuation (due to any reason) – treatment policy Use of systemic antimicrobials – composite strategy
Clinical outcome at the TOC and Follow-up Visits	Female participants with acute cystitis with qualifying bacterial uropathogen(s) at baseline that all are susceptible to nitrofurantoin	Gepotidacin 1500 mg BID for 5 days versus nitrofurantoin 100 mg BID for 5 days, regardless of adherence	See Table 5	Percentage of participants in each outcome category in the gepotidacin and nitrofurantoin arms separately	Study treatment discontinuation (due to any reason) – treatment policy Use of systemic antimicrobials – composite strategy

Secondary Endpoint	Population	Treatment Condition	Variable	Summary Measure	Intercurrent Event

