- **Follow-up (Day 28±3) Visit.** Participants will be instructed to return to the study site 28 (±3) days postrandomization in order to complete the Follow-up Visit. Assessments will be performed as shown in Section 1.3, including the following:
 - The Follow-up Visit will be preceded by a documented reminder contact from the study site to the participant 24 ±4 hours before the scheduled appointment time per the method (e.g., text message, telephone call, e-mail) confirmed with the study site staff prior to departing the study site on Day 1.
 - Specimens for microbiological testing will be collected, as described in Section 8.1. Clinical signs and symptoms of acute cystitis will be recorded, as described in Section 8.1.3.1 and Appendix 6. CCI
[REDACTED]
[REDACTED]
 - Participants experiencing signs and symptoms suggestive of infection recurrence or relapse will be assessed and treated per the investigator's judgement.

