7.2.1.2. Clinical Outcome and Response at TOC and Follow-Up

Clinical outcome and response are evaluated at participant level at the TOC and FU Visits. The criteria for clinical outcome and response are defined in [Table 8](#) (TOC) and similarly in [Table 11](#) (FU).

Table 11 Clinical Outcome and Response at the Follow-Up Visit

Defining Criteria	Outcome	Response
Participants who withdraw from the study prior to the FU Visit will be considered not achieving success (imputed as failure) as the clinical response at FU.		
Resolution of signs and symptoms of acute cystitis demonstrated at the TOC Visit persist at the FU Visit (and no new signs and symptoms), without the participant receiving other systemic antimicrobials before the FU Visit.	Sustained clinical resolution	Clinical success
Resolution of signs and symptoms of acute cystitis present at Baseline (and no new signs or symptoms), after clinical failure at TOC, without the participant receiving other systemic antimicrobials before the FU Visit.	Delayed clinical resolution	Clinical failure
Improvement in total symptom scores from Baseline, but not complete resolution, without the participant receiving other systemic antimicrobials before the FU Visit.	Clinical improvement	Clinical failure
Worsening or no change in total symptom scores at FU compared to Baseline after clinical failure at TOC or the participant received other systemic antimicrobials for the current infection before or on the date of the FU Visit	Clinical worsening	Clinical failure
Signs and symptoms of acute cystitis reoccur at the FU Visit assessment after clinical success at the TOC Visit	Clinical recurrence	Clinical failure
1) The baseline score is missing or 2) The FU assessment is missing or 3) The participant received other systemic antimicrobials not for the current infection before the FU Visit (unless clinical worsening or recurrence outcome criteria were met)	Unable to determine	Clinical failure

TOC=Test-of-Cure. FU=Follow-up.

If participant took both other systemic antimicrobials for the current infection on or before the date of the FU Visit, and other systemic antimicrobials not for the current infection before the date of the FU Visit, then participant outcome will be derived as ‘Clinical worsening’.

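### At Follow-up, a relapse after Test-of-Cure success that was treated and has resolved can only be classed as clinical worsening or unable to determine; one treated but still symptomatic can meet both worsening and recurrence, with no ranking

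*Protocol*

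**What the plan says.** Protocol Section 8.1.3.1 (Table 11) and SAP Section 7.2.1.2 (Table 11) define clinical outcome at Follow-up by rows, and the outcome is derived by program.

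- **Clinical worsening** has two limbs. The symptom limb is "Worsening or no change in total symptom scores at Follow-up compared to Baseline after clinical failure at TOC". The antimicrobial limb follows directly: "or the participant received other systemic antimicrobials for the current infection before or on the date of the Follow-up Visit". The SAP repeats it: "the participant received other systemic antimicrobials for the current infection before or on the date of the FU Visit".
- **Clinical recurrence** in the protocol is "Signs and symptoms of acute cystitis reoccur at the Follow-up Visit after clinical success at TOC". In the SAP it is "Signs and symptoms of acute cystitis reoccur at the FU Visit assessment after clinical success at the TOC Visit". Neither version excludes participants who took an antimicrobial.
- **Unable to determine** covers, among other things, an antimicrobial taken for something other than the current infection, "unless the clinical worsening or recurrence outcome criteria were met". The SAP row has an equivalent exception.
- A note under SAP Table 11 assigns *clinical worsening* to a participant who took antimicrobials both for the current infection and for another reason.

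The protocol expects treatment of relapses. Section 8 says of the Follow-up Visit: "Participants experiencing signs and symptoms suggestive of infection recurrence or relapse will be assessed and treated". Section 8 also lets participants return at any time with new symptoms and be treated.

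Protocol Table 1 gives the summary measure for this secondary endpoint: "Percentage of participants in each outcome category in the gepotidacin and nitrofurantoin arms separately".

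**The concern.** Apart from the antimicrobial limb, the worsening and recurrence rows separate Follow-up failures by what happened at TOC: worsening by symptoms for those who had failed, recurrence for those who had succeeded. The antimicrobial limb breaks that separation. It places participants who were cured and then relapsed alongside participants who never responded.

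Table 10 makes the mixing plain. Anyone given an antimicrobial for the current infection before or on the TOC date is already a clinical failure at TOC. So a TOC success who meets the antimicrobial limb at Follow-up must have been treated after her symptoms were documented as resolved.

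What is at stake is the meaning of the category percentages. They are the summary measure of this endpoint, so the categories should be mutually exclusive and a relapse should be recognisable as one.

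**Working it through.** The documents give no recurrence figure to reproduce. The check is to apply each row of Table 11 literally.

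**Step 1. Rows met by a participant with clinical success at TOC who then takes an antimicrobial**

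| Antimicrobial recorded as for | Symptoms at Follow-up | Rows met |
|---|---|---|
| Current infection | None | Worsening only |
| Current infection | Present, milder than Baseline | Worsening and recurrence |
| Current infection | Same as or worse than Baseline | Worsening and recurrence |
| Current infection | Assessment missing | Worsening and unable to determine |
| Another reason | None | Unable to determine |
| Another reason | Present | Recurrence |

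Only the first line is forced into worsening by the text. Lines two and three, which include a relapse found and treated on the Follow-up date, are undecided. The protocol exception ranks worsening and recurrence above *unable to determine* but not against each other. The SAP note covers only participants who took both kinds of antimicrobial.

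**Step 2. Other evidence of the relapse can drop out.** SAP Section 5.6 sets the TOC analysis window at Days 9 to 16 and the Follow-up window at Days 21 to 31, with target Day 28. A symptom score on Days 17 to 20 belongs to neither visit. If she scores symptoms on Day 22 and none on Day 28, the Day 28 record is used. The antibiotic is then the only remaining trace, and it maps to worsening.

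**Step 3. Microbiological table.** In Protocol Table 4 and SAP Table 9, any other systemic antimicrobial before the Follow-up Visit gives *unable to determine*. A relapse treated before the visit is therefore not shown as microbiological recurrence either. These rows say before the visit, not on its date, so a participant cultured and then treated at the visit can still be a microbiological recurrence.

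**Step 4. Current infection.** Table 11 does not say whether a new cystitis episode after TOC success counts. SAP Section 2.4 describes antimicrobials for the current infection as rescue treatment and sets them against treatment for other infections. SAP Section 6.1.3 splits antibiotics by disease under study against another condition. A cystitis relapse fits the first side of each split better. On the other reading, a symptomatic participant is recurrence and a symptom-free one is unable to determine.

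**Step 5. Illustration, on assumed inputs only.** Let r be the true recurrence proportion, q the share treated for the current infection by the Follow-up date, and s the share of those treated who are still symptomatic at Follow-up. Assume untreated relapses are symptomatic at Follow-up.

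- Worsening programmed first: recorded recurrence = r(1 − q).
- Recurrence programmed first: recorded recurrence = r(1 − q) + rqs.
- Loss forced by the text = rq(1 − s). Loss that depends on the ranking = rqs.

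With r = 10% and q = 80%:

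- Worsening first: 0.10 × 0.20 = 2.0%.
- Recurrence first: 2.0% + 8.0% × s, which is 2.0% at s = 0, 6.0% at s = 0.5 and 10.0% at s = 1.

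The range over the assumptions:

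| r | q | Worsening first | Recurrence first (s from 0 to 1) |
|---|---|---|---|
| 5% | 80% | 1.0% | 1.0% to 5.0% |
| 10% | 50% | 5.0% | 5.0% to 10.0% |
| 10% | 80% | 2.0% | 2.0% to 10.0% |
| 10% | 100% | 0% | 0% to 10.0% |
| 15% | 80% | 3.0% | 3.0% to 15.0% |

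**Step 6. Response.** Worsening, recurrence and unable to determine all map to clinical failure. No success rate changes in any scenario.

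**The case against.** The strongest reply is that little turns on this.

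- The categories are descriptive. Protocol Section 3 plans no direct comparison between arms for outcomes, and SAP Section 7.2.6.1 plans no formal testing of secondary endpoints.
- Durability is shown by clinical response at Follow-up, where success means sustained resolution. It is reported with an adjusted difference and 95% CI.
- Reasons for failure, including non-study antibacterial therapy, are tabulated by arm. Antibiotics for the disease under study are summarised and listed.
- No recurrence-rate endpoint is defined, and the recurrence row describes status at the visit.
- Tables 9, 10 and 11 all place antimicrobials for the current infection under worsening, so the rule is at least consistent.

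Most of this stands, and it limits the point to a modest one. It does not remove it. Tables 9 and 10 have no recurrence category to protect; Table 11 does. The plan also does not say that the reasons-for-failure summary is split by TOC response, so it would not clearly recover the relapses.

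A reader might infer that every treated recurrence is filed as worsening. The documents do not support that: the recurrence row has no antimicrobial exclusion, so those still symptomatic meet it too. A reader might also take the note under SAP Table 11 as the only tie-break in favour of worsening. The *unable to determine* row already yields to recurrence as well as to worsening.

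**Conclusion.** The point holds in limited form. A participant with TOC success whose relapse was treated and had resolved by Follow-up cannot be counted as clinical recurrence under either Table 11. For one still symptomatic after treatment for the current infection, the rows overlap without a ranking, and understatement follows only if worsening is programmed first. In both cases, classification as worsening requires the relapse to count as the current infection, which Table 11 leaves undefined.

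The size cannot be derived from the documents. A reader might try the Phase IIa counts in Protocol Section 2.1, where 19 of 22 were resolved at TOC and 18 of 22 at Follow-up, and take 1/19 = 5.3% as the recurrence rate. That is a net difference of one participant, not a count of relapses among TOC successes. It says nothing about how many relapses were treated or still symptomatic.

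Nor do the documents support saying that such relapses never appear as recurrence in either Follow-up table, given the on-the-day case in Step 3, or that the comparison of durability between arms is lost. Clinical response, therapeutic response and the primary TOC endpoint do not change. Only the split of Follow-up failures by category is affected.

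**What to change.** In Table 11 of both the protocol and the SAP:

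1. Limit the antimicrobial limb of *clinical worsening* to participants with clinical failure at TOC.
2. For participants with clinical success at TOC, classify as *clinical recurrence* either symptoms of acute cystitis at Follow-up, or other systemic antimicrobials received for acute cystitis after TOC and before or on the Follow-up date.
3. State that, for TOC successes, recurrence takes precedence over worsening and over *unable to determine*. Make the note under SAP Table 11 subject to this.
4. State that current infection includes a recurrent cystitis episode after TOC.

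Leave the response column as it is.

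The cost is wording in two tables and a small programming change, with no new data. The downside is that some recurrences would rest on treatment for cystitis without a scored symptom assessment, for example where treatment followed a positive culture. A footnote giving the number assigned that way in each arm would make this visible.

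A related overlap needs no antimicrobial: a TOC success with symptoms milder than Baseline at Follow-up meets both *clinical improvement* and *clinical recurrence*. The same precedence statement could settle it.

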8.2. Safety Assessments

Planned time points for all safety assessments are provided in the SoA (Section 1.3).

8.2.1. Physical Examinations

- A physical examination will be performed at the time points indicated in the SoA (Section 1.3).
- At Baseline, the examination will include assessments of the respiratory, CV, abdominal, gastrointestinal, neurological, and urogenital systems. Height and weight will only be measured and recorded at the Baseline Visit (before dosing).
- At the TOC Visit, the physical examination may be symptom directed and is only required if indicated for a specific participant.
- Investigators should pay special attention to clinical signs related to previous serious illnesses.
- Clinically significant changes from baseline or clinically significant new clinical signs will be reported as AEs.

8.2.2. Vital Signs

- Vital signs will be measured at the time points indicated in the SoA (Section 1.3).
- Vital signs will be measured in a semi-supine position after 5 minutes rest and will include temperature, systolic and diastolic blood pressure, and pulse rate.

- Vital sign measurements should be obtained before any blood draws scheduled on the same assessment day.
- Clinically significant changes from baseline will be reported as AEs.

8.2.3. Electrocardiograms

- Electrocardiograms will be performed at the time points indicated in the SoA (Section 1.3).
- Triplicate 12-lead ECGs (over an approximate 5- to 10-minute period) will be performed using an ECG machine that automatically calculates the heart rate and measures PR, QRS, QT, and QTc intervals. Refer to Section 7.1.2 for QTc withdrawal criteria and additional QTc readings that may be necessary.
- Ideally, ECGs will be obtained before any vital sign measurements or blood draws scheduled on the same assessment day; however, sites may perform procedures in an order per their standard of care, as long as participants return to a resting state prior to the start of the ECG collections.
- Triplicate ECGs will be performed at Baseline.
- For the first approximately 1200 participants enrolled, On-therapy Visit triplicate ECGs will also be obtained. The On-therapy ECGs will be collected approximately 2 hours postdose (i.e., expected time of maximum concentration; ECG collection should ideally be within approximately 1.5 hours postdose to 4 hours postdose). After the first approximately 1200 participants have triplicate ECGs performed at On-therapy, the ECG collection at this visit is no longer a protocol requirement.
- If any additional ECGs are performed during the study (if deemed necessary by the investigator), those may be collected as a single ECG; however, if that initial single reading shows QTc prolongation, then triplicate ECGs should also be performed (see Section 7.1.2).
- If clinically significant changes occur during the study, they will be reported as AEs.
- Electrocardiograms will be reviewed locally by the investigator for safety purposes. Electrocardiograms will be centrally overread for the data analysis.

